10.6.1 Follow-up of subjects after study participation has ended

Following this study, the subject will return to their eye care professional for their routine eye care.

11 ADVERSE EVENTS AND DEVICE DEFICIENCIES

11.1 General Information

An AE is any untoward medical occurrence, unintended disease or injury, or untoward clinical signs (including abnormal laboratory findings) in subjects, users, or other persons, whether or not related to the investigational medical device (test article). Refer to the Glossary of Terms and figures below for categories of AEs and SAEs.

Figure 11–1 Categorization of All Adverse Events

[figure not shown]
[figure not shown]

Figure 11–2 Categorization of All Serious Adverse Events***Serious Adverse Events***

In addition to reporting all AEs (serious and non-serious) meeting the definitions, the Investigator must report any occurrence of the following as an SAE:

- An ocular infection including a presumed infectious ulcer with any of the following characteristics*:
 - Central or paracentral location
 - Penetration of Bowman’s membrane
 - Infiltrates > 2 mm diameter
 - Iritis
 - Increase in intraocular pressure
 - Culture positive for microorganisms
 - Increasing size or severity at subsequent visits
- Any central or paracentral corneal event (such as neovascularization) that results in permanent opacification
- Hypopyon

- Hyphema
- Neovascularization within the central 6 mm of the cornea
- Permanent vision loss as defined by loss of 2 or more lines of BCVA from enrollment visit that fails to resolve
- Uveitis (anterior, intermediate, or posterior)
- Corneal abrasion affecting $\geq 50\%$ of corneal surface area

*NOTE: Culture samples (from the subject's eyes, lenses, etc) must be taken at investigator's discretion [*as described in the MOP; and documented in the narrative section(s) of the corresponding ADE-SAE eCRF*], for any suspected ocular infection, including infiltrates with overlying epithelial defect.

Significant Non-Serious Adverse Events

A significant non-serious AE is a device-related, non-sight threatening AE that warrants discontinuation of any contact lens wear for greater than or equal to 2 weeks. In addition, the Investigator must report any occurrence of the following as a Significant Non-Serious Adverse Event:

- Peripheral non-progressive non-infectious ulcers
- All symptomatic corneal infiltrative events
- Corneal staining score greater than or equal to Grade 3 (Refer to MOP for grading scales)
- Temporary vision loss as defined by loss of 2 or more lines of BCVA from enrollment visit that persists for 2 or more weeks
- Neovascularization score greater than or equal to Grade 2 (Refer to MOP for grading scales)

The above events are based upon the categories provided in ISO 11980 and the US FDA Premarket Notification (510(k)) Guidance Document for Daily Wear Contact Lenses.

Device Deficiencies

A device deficiency is inadequacy of a medical device with respect to its identity, quality, durability, reliability, safety, or performance. A device deficiency may or may not be associated with subject harm (ie, ADE or SADE); however, not all ADEs or SADEs are due to a device deficiency. The Investigator should determine the applicable category listed in the

Device Deficiency eCRF for the identified or suspect device deficiency and report any subject harm separately. Examples of device deficiencies include the following:

- Failure to meet product specifications (eg, incorrect lens power/diameter/base curve/color)
- Lens cloudy
- Lens surface/edge defect
- Torn lens during handling/in pack
- Packaging deficit (eg, mislabeled product)
- Suspect product contamination
- Lack of performance

11.2 Monitoring for Adverse Events

At each visit, after the subject has had the opportunity to spontaneously mention any problems, the Investigator should inquire about AEs by asking the standard questions:

- “Have you had any health problems since your last study visit?”
- “Have there been any changes in the medicines you take since your last study visit?”

Changes in *any protocol-specific parameters and/or questionnaires* evaluated during the study are to be reviewed by the Investigator. Any untoward (unfavorable and unintended) change in *a protocol-specific parameter or questionnaire response* that is clinically relevant, in the opinion of the Investigator, is to be reported as an AE. These clinically relevant changes will be reported regardless of causality.

11.3 Procedures for Recording and Reporting

AEs are collected from the time of informed consent. Any pre-existing medical conditions or signs/symptoms present in a subject prior to the start of the study (ie, before informed consent is signed) are not considered AEs in the study and should be recorded in the Medical History section of the eCRF.

In addition, temporary lens awareness or visual changes during the fitting process are not considered AEs if the Investigator assesses that the symptom(s) can reasonably resolve within the anticipated adaptation period.

- ADEs or SAEs are documented on the *Serious Adverse Event and Adverse Device Effect* eCRF within 24 hours of the Investigator's or site's awareness.
- Device deficiencies are documented on the *Device Deficiency* eCRF within 24 hours of the Investigator's or site's awareness.
- A printed copy of the completed *Serious Adverse Event and Adverse Device Effect* and/or *Device Deficiency* eCRF must be included with product returns.
- Additional relevant information after initial reporting must be entered into the eCRF as soon as the data become available.
- Document any changes to concomitant medications on the appropriate eCRFs.
- Document all relevant information from Discharge Summary, Autopsy Report, Certificate of Death, etc, if applicable, in narrative section of the *Serious Adverse Event and Adverse Device Effect* eCRF.

Note: Should the EDC system become non-operational, the site must complete the appropriate paper *Serious Adverse Event and Adverse Device Effect* and/or *Device Deficiency* Form. The completed form is emailed to the Study Sponsor at [REDACTED] according to the timelines outlined above; however, the reported information must be entered into the EDC system once it becomes operational.

Additionally, any AEs and device deficiencies for non-study marketed devices/products (ie, CLEAR CARE Cleaning and Disinfecting Solution, LacriPure (or equivalent), and Systane preservative-free eye drops) will be considered and processed as spontaneous (following the postmarket vigilance procedures) and should be communicated to the device's/product's manufacturer as per local requirements.

Study Sponsor representatives may be contacted for any protocol related question; their contact information is provided in the MOP that accompanies this protocol.

Further, depending upon the nature of the AE or device deficiency being reported, the Study Sponsor may request copies of applicable portions of the subject's medical records. The Investigator must also report all AEs and device deficiencies that could have led to a SADE according to the requirements of regulatory authorities or IRB/IEC.

Intensity and Causality Assessments

Where appropriate, the Investigator must assess the intensity (severity) of the AE based upon medical judgment with consideration of any subjective symptom(s), as defined below:

Intensity (Severity)

- Mild** An AE is mild if the subject is aware of but can easily tolerate the sign or symptom.
- Moderate** An AE is moderate if the sign or symptom results in discomfort significant enough to cause interference with the subject's usual activities.
- Severe** An AE is severe if the sign or symptom is incapacitating and results in the subject's inability to work or engage in their usual activities.

For every AE in the study, the Investigator must assess the causality (Related or Not Related to the medical device or study procedure). An assessment of causality will also be performed by Study Sponsor utilizing the same definitions, as shown below:

Causality

- Related** An AE classified as related may be either definitely related or possibly related where a direct cause and effect relationship with the medical device or study procedure has not been demonstrated, but there is a reasonable possibility that the AE was caused by the medical device or study procedure.
- Not Related** An AE classified as not related may either be definitely unrelated or simply unlikely to be related (ie, there are other more likely causes for the AE).

The Study Sponsor will assess the AEs and may upgrade the Investigator's assessment of seriousness and/or causality. The Study Sponsor will notify the Investigator of any AEs that are upgraded from non-serious to serious or from unrelated to related.

Additionally, the Study Sponsor shall immediately conduct an evaluation of any unanticipated adverse device effect, including anticipated adverse events that occur in unanticipated severity or frequency. The results of this evaluation will be reported to the FDA, the IRB, and participating Investigators within 10 working days upon receiving notification of the effect.

11.4 Return product analysis

Investigational product associated with device deficiencies and/or product related AEs [ie, ADE or SADE] will be returned for investigation as detailed in the MOP.

11.5 Unmasking of the Study Treatment

Masked information on the identity of the assigned medical device should not be disclosed during the study. If the treatment code needs to be broken in the interest of subject safety, the Investigator is encouraged to contact an appropriate Study Sponsor representative prior to unmasking the information if there is sufficient time. Dependent upon the individual circumstances (ie, medical emergency), the code may be broken prior to contact with the Study Sponsor. The Study Sponsor must be informed of all cases in which the code was broken and of the circumstances involved. Additionally, the Study Sponsor may be required to unmask the information in order to fulfill expedited regulatory requirements.

11.6 Follow-Up of Subjects with Adverse Events

The Investigator is responsible for adequate and safe medical care of subjects during the study and for ensuring that appropriate medical care and relevant follow-up procedures are maintained after the study.

The Investigator should provide the Study Sponsor with any new safety information (which includes new AEs and changes to previously reported AEs) that may affect the safety evaluation of the device. For AEs that are unresolved/ongoing at time of subject exit from study, any additional information received at follow-up should be documented in the eCRFs up to study completion (ie, database lock).

Any additional data received up to 3 months after subject discontinuation or exit must be documented and available upon the Study Sponsor's request. All complaints received after this time period will be considered and processed as spontaneous (following the postmarket vigilance procedures) and should be communicated to the medical device's manufacturer as per local requirements, as applicable.

The Investigator should also report complaints on non-Alcon products directly to the manufacturer as per the manufacturer's instructions or local regulatory requirements.

11.7 Pregnancy in the Clinical Study

Pregnancy is not reportable as an AE; however, complications may be reportable and will be decided on a case-by-case basis. Should a woman become pregnant during study participation, the pregnancy will be documented on the Medical History eCRF.

12 ANALYSIS PLAN

Any deviations to the analysis plan will be updated during the course of the study as part of a protocol amendment or will be detailed in the clinical study report.

All analyses will be conducted according to the applicable statistical analysis plan.

12.1 Subject Evaluability

Final subject evaluability must be determined prior to breaking the code for masked treatment (lens) assignment and locking the database, based upon the Deviations and Evaluability Plan.

12.2 Analysis Sets

Five analysis sets will be defined:

- a) All Enrolled – all subjects signing the informed consent form
- b) Enrolled Dispensed – subjects/eyes from All Enrolled that have been exposed to study lenses [REDACTED]
- c) Enrolled Not Dispensed – subjects/eyes from All Enrolled that have not been exposed to study lenses [REDACTED]
- d) Completed – Enrolled Dispensed subjects/eyes completing the study
- e) Discontinued – Enrolled Dispensed subjects/eyes not completing the study

12.3 Demographic and Baseline Characteristics

Demographic information, recent lens-wearing experience (including wear modality and wear success), and habitual lens information will be presented by lens group and overall for the All Enrolled analysis set.

Baseline data will be summarized by lens group, for Completed and Discontinued analysis sets separately, as applicable.

12.4 Effectiveness Analyses

For the primary [REDACTED] endpoint, separate summaries will be prepared, when applicable, for the Completed and the Discontinued analysis sets as follows:

- Completed Control (eyes/subjects)
- Completed Test (eyes/subjects)

- Discontinued Control (eyes/subjects)
- Discontinued Test (eyes/subjects)

No inferential testing will be performed on effectiveness endpoints, and format of the reporting tables will reference FDA's 510(k) guidance document (Clinical Appendix C, Summary of Reporting Tables) as well as the ISO guidance as specified in section A.3 (Reporting of results) of ISO 11980:2012.

12.4.1 Analysis of Primary Effectiveness Endpoint(s)

[figure not shown]
[figure not shown]
The primary effectiveness endpoint is distance VA with study lenses, collected in Snellen, for each eye. Conversion will be made to the logMAR scale.

[figure not shown]
[figure not shown]
12.4.1.1 Statistical Hypotheses

No hypothesis testing on the primary effectiveness endpoint is planned.

12.4.1.2 Analysis Methods

Summary statistics will be provided. [REDACTED]

12.6 Safety Analyses

All AEs occurring from the time a subject signs informed consent to study exit will be accounted for in the reporting. Safety analyses will be conducted using the safety analysis set on a treatment-emergent basis. Descriptive summaries (counts and percentages) and listings will be presented. Individual subject listings will be provided for AEs that occur after signing informed consent but prior to exposure to IP.

12.6.1 Analysis of Primary Safety Endpoint(s)

The primary safety endpoint is the proportion of ocular serious and significant non-serious ADEs, calculated as the number of eyes reporting at least one treatment-emergent device-related ocular serious ADE or treatment-emergent device-related ocular significant non-serious ADE.

12.6.1.1 Statistical Hypotheses

The null and alternative hypotheses for the primary analysis are:

$$H_0: P_T - P_C \geq 0.05$$

$$H_a: P_T - P_C < 0.05$$

where P_T and P_C denote the proportion of eyes reporting ocular serious and significant non-serious ADEs with [REDACTED] and Biofinity contact lenses, respectively.

12.6.1.2 Analysis Methods

A generalized linear model, with a logit link function, accounting for within-subject correlation will be fit. A one-sided 95% upper confidence limit (UCL) will be calculated for the difference in proportions between treatments ([REDACTED] contact lens minus Biofinity contact lens), and the null hypothesis will be rejected if $UCL < 0.05$.

12.6.2 Analysis of Other Safety Endpoints

Other safety endpoints include:

- AE (non-serious, non-significant)
- Biomicroscopy findings
- Device deficiencies

12.6.2.1 Statistical Hypotheses

No hypothesis testing on the other safety endpoints is planned.

12.6.2.2 Analysis Methods

Descriptive summaries (counts and percentages) for ocular and nonocular AEs will be presented by Medical Dictionary for Regulatory Activities Preferred Terms, for Completed and Discontinued analysis sets. A listing containing details of the AEs will also be provided.

[figure not shown]
Each biomicroscopy parameter will be tabulated by its grade, on Completed and Discontinued analysis sets. Frequency for each device deficiency category will be presented and a supporting listing will be provided.

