
Data analysis and sample size justification
	
In adherence to the reporting format as specified in the ISO clinical standard and FDA 510(k) guidance documents, effectiveness and safety data of the primary cohort will be presented separately based upon subject study status of Completed or Discontinued.
 
The primary safety analysis is to assess noninferiority of  contact lenses when compared to Biofinity contact lenses for the proportion of ocular serious and significant non-serious ADEs, with a pre-defined margin of 0.05 (5%). A generalized linear model with a logit link function will be used, and a one-sided 95% upper confidence limit (UCL) will be calculated for the difference in proportions between treatments ( minus Biofinity).

	
No formal hypotheses are formulated for the primary effectiveness endpoint of distance VA; hence, no inferential testing will be performed. Descriptive summary statistics will be provided for the Snellen categories as well as the converted logMAR values.
 
[REDACTED]
 
The sample size calculation was based on previous extended wear clinical studies which evaluated five currently marketed silicone hydrogel lenses. Assuming that the expected difference between test and control is 0 and that the control proportion is 0.045, a sample size of 213 per group will provide 80% power to reject the null hypothesis of inferiority in test compared to control, with a noninferiority margin of 0.05 (5%).

Key words	[REDACTED] Biofinity, extended wear
Associated materials	CLEAR CARE and LaciPure (or equivalent) will be permitted if the subject must remove their lens(es) for any reason. Systane will be also be permitted but should only be used if necessary.

[figure not shown]
Table 3-1 Schedule of Study Procedures and Assessments^a

Procedure/Assessment	Baseline	Follow-Up Visits								Exit	Early Exit	USV
	Visit 1	Visit 2	Visit 3	Visit 4	Visit 5	Visit 6	Visit 7	Visit 8	Visit 9			
	Day 1 Dispense	24 hrs Day 2 ± 4 hrs	1-week Day 7 ± 2 d	1-month Day 30 ± 4 d	2-months Day 60 ± 7 d	3-months Day 90 ± 7 d	6-months Day 189 -7 / + 14 d	9-months Day 270 ± 14 d	12-months Day 365 ± 14 d			
Informed Consent	✓	-	-	-	-	-	-	-	-	-	-	-
Demographics	✓	-	-	-	-	-	-	-	-	-	-	-
Medical History including pregnancy ¹	✓	✓	✓	✓	✓	✓	✓	✓	✓	✓	✓	(✓)
Concomitant Medications	✓	✓	✓	✓	✓	✓	✓	✓	✓	✓	✓	(✓)
Inclusion/Exclusion	✓	-	-	-	-	-	-	-	-	-	-	-

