10.5.2 Discontinuations

Discontinued subjects are individuals who voluntarily withdraw or are withdrawn from the study by the Investigator after signing the informed consent.

Subject numbers of discontinued subjects must not be re-used.

Subjects may discontinue from study or study treatment at any time for any reason. Subjects may also be discontinued from study treatment at any time if, in the opinion of the Investigator, continued treatment poses a risk to their health.

Subjects missing consecutive follow-up visits will be evaluated to determine if discontinuation may be necessary.

For subjects discontinuing from the study, the Investigator must complete all Exit procedures according to Table 3-1, if the subject is willing and able, and if in the opinion of the Investigator it is safe for the subject to do so.

The Investigator must document the reason for study or treatment discontinuation in the subject's case history source documents.

To ensure the safety of all subjects who discontinue early, Investigators must assess each subject and, if necessary, advise them of any therapies and/or medical procedures that may be needed to maintain their health.

10.5.3 Schedule of Procedures and Assessments for Subjects Discontinued from Investigational Product

Other than screen failures, if a subject discontinues from the study, the subject should undergo an Early Exit Visit. Refer to Table 3-1.

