2.4 Completed

The Completed analysis set consists of Enrolled Dispensed subjects/eyes completing the study.

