4.6 Interim Analysis for Effectiveness

No interim analysis is planned for effectiveness endpoints.

5 Safety Analysis Strategy

Unless otherwise specified, separate summary tables will be presented for the Completed and the Discontinued analysis sets with the following distinction:

- Completed Control (eyes/subjects)
- Completed Test (eyes/subjects)
- Discontinued Control (eyes/subjects)
- Discontinued Test (eyes/subjects)

Subjects/eyes will be categorized under the actual lens exposed.

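### Adverse event and slit-lamp tables are visibly assigned only to the Completed and Discontinued sets, while Protocol 12.6 relies on an undefined safety analysis set; add a by-lens column over all dispensed eyes

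*Protocol*

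**What the plan says.** - **Tables by final status.** Protocol 12.6.2.2 summarizes AEs by preferred term "for Completed and Discontinued analysis sets". For the slit lamp it says: "Each biomicroscopy parameter will be tabulated by its grade, on Completed and Discontinued analysis sets".
- **SAP default.** SAP section 5 states that, unless something else is specified, "separate summary tables will be presented for the Completed and the Discontinued analysis sets with the following distinction": Completed Control, Completed Test, Discontinued Control, Discontinued Test. The visible text of SAP 5.3.2.1 (AEs) and 5.3.3 (slit lamp) names no other set.
- **Reason for the layout.** The Protocol Summary (section 3) says "effectiveness and safety data of the primary cohort will be presented separately based upon subject study status of Completed or Discontinued" and gives the ISO and FDA 510(k) reporting format as the reason.
- **Contrary text.** Protocol 12.6 says: "Safety analyses will be conducted using the safety analysis set on a treatment-emergent basis". Protocol 12.2 begins "Five analysis sets will be defined" and lists All Enrolled, Enrolled Dispensed, Enrolled Not Dispensed, Completed and Discontinued. A safety set is not among them, and the visible SAP does not use the term.
- **How the sets relate.** SAP 2.4: "The Completed analysis set consists of Enrolled Dispensed subjects/eyes completing the study". SAP 2.5 puts the remaining dispensed subjects/eyes in Discontinued.
- **What drives the split.** Protocol 10.5.2 allows discontinuation for any reason, and also where the investigator judges that "continued treatment poses a risk to their health". The listings in SAP 5.3.2.1 mark AEs that led to study discontinuation.

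**The concern.** Whether an eye belongs to Completed or Discontinued is known only at the end of follow-up, and an AE is one of the things that can decide it. The denominator of each AE percentage is therefore partly selected by the outcome being tabulated. For slit-lamp grades, which SAP 5.3.3 tabulates visit by visit, the selection looks forward in time: the 1-month Completed column leaves out eyes that drop out later, possibly because of what was seen, and those eyes sit in a separate Discontinued table.

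Randomization balances the lenses over all randomized subjects, and very nearly over all dispensed ones. It does not balance them within subgroups formed by a later event. If the lenses differ in how often an AE ends in discontinuation, the within-set percentages can differ without any difference in AE rate. Protocol 5.3 says the study will evaluate how the risks of the new lens compare with a marketed lens. For AEs outside the primary composite and for slit-lamp findings, these descriptive tables are where that comparison will be read.

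The sentence in Protocol 12.6 does not settle the matter. It points to a single set that is not defined, while the sections that specify the tables name two others.

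**Working it through.** **1. The passages side by side.** Protocol 12.6 names one safety set, undefined. Protocol 12.6.2.2, SAP section 5 and the Protocol Summary name Completed and Discontinued. Protocol section 12 says analyses follow the SAP, so on the visible text the four-cell layout governs the AE and slit-lamp tables. Enrolled Dispensed is defined, but no visible AE or slit-lamp table is assigned to it.

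**2. The plan's own figures.** The drop-out used below comes from Protocol 12.8. With control rate 0.045, expected difference 0, margin 0.05 and one-sided 95% limit:

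- SE at 213 per group = √(2 × 0.045 × 0.955 / 213) = 0.0201
- 0.05 / 0.0201 − 1.645 ≈ 0.844, giving power 80.07%
- 213 / 0.75 = 284 per group

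Both stated figures reproduce and are not in dispute.

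**3. Formulas.** Let p be the true AE rate, d the probability of discontinuing given an AE, and D the total drop-out.

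- Percentage shown in Completed = p(1 − d) / (1 − D)
- Percentage shown in Discontinued = p·d / D
- Pooled = (1 − D) × Completed + D × Discontinued = p

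**4. Inputs.** D = 0.25 in both arms is the planning figure. The documents give neither p nor d; both are assumptions.

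**5. Worked example.** p = 0.10 in both arms; d = 0.60 test, 0.40 control.

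- Completed, test: 0.10 × 0.40 / 0.75 = 5.3%; control: 0.10 × 0.60 / 0.75 = 8.0%
- Discontinued, test: 0.10 × 0.60 / 0.25 = 24%; control: 0.10 × 0.40 / 0.25 = 16%
- Pooled, test: 0.04 + 0.06 = 10%; control: 0.06 + 0.04 = 10%

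The inputs are mutually consistent. Drop-out among eyes without an AE would be (0.25 − 0.06) / 0.90 = 21.1% on test and (0.25 − 0.04) / 0.90 = 23.3% on control.

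**6. Range** (test versus control, D = 0.25 in both arms, equal true rates):

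| p | d test / control | Completed | Discontinued | Pooled |
|---|---|---|---|---|
| 10% | 0.40 / 0.40 | 8.0% vs 8.0% | 16% vs 16% | 10% vs 10% |
| 10% | 0.60 / 0.40 | 5.3% vs 8.0% | 24% vs 16% | 10% vs 10% |
| 10% | 0.80 / 0.40 | 2.7% vs 8.0% | 32% vs 16% | 10% vs 10% |
| 5% | 0.60 / 0.25 | 2.7% vs 5.0% | 12% vs 5% | 5% vs 5% |
| 10% | 0.60 / 0.25 | 5.3% vs 10.0% | 24% vs 10% | 10% vs 10% |
| 20% | 0.60 / 0.25 | 10.7% vs 20.0% | 48% vs 20% | 20% vs 20% |

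The first row shows the limit of the point: with equal d and equal D the tables agree. Unequal drop-out for other reasons can also separate them. With p = 0.10 and d = 0.50 in both arms, but drop-out without an AE of 15% versus 25%, D is 18.5% versus 27.5%. Completed then reads 0.05 / 0.815 = 6.1% versus 0.05 / 0.725 = 6.9%, and Discontinued 0.05 / 0.185 = 27.0% versus 0.05 / 0.275 = 18.2%.

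**The case against.** The strongest reply is that nothing is lost. Completed and Discontinued together make up Enrolled Dispensed, counts are planned in four labelled cells by lens, and anyone can add the cells if the denominators are shown. That stands, and it makes this a matter of presentation and consistency. It does not make the printed percentages the right ones to compare, and it leaves the relevant comparison to the reader's own arithmetic.

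The layout is also deliberate, following a stated regulatory format. That is a reason to keep the tables, not a reason to omit a pooled column.

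The examples need d to differ between lenses in a double-masked trial. Moreover, device-related events warranting two weeks or more without lens wear are classed as significant, so a d of 60% to 80% may be high for the non-serious, non-significant AEs that remain. This is fair, and it is why no size can be claimed.

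Four stronger readings are tempting but unsupported:

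- **That no pooled by-lens table is planned.** Protocol 12.6 invokes a safety set, the SAP split is only a default, and content is withheld near Protocol 12.6.2.2 and SAP 5.3.2.1. A pooled table cannot be excluded.
- **That AEs cause the split.** They are one cause among others; the 25% is not broken down by reason.
- **That the tables will reverse the comparison or hide an excess on the test lens.** Reversal in both tables can be constructed: test 8/190 and 26/94 against control 12/240 and 13/44 gives 4.2% vs 5.0% and 27.7% vs 29.5%, but 34/284 = 12.0% vs 25/284 = 8.8% pooled. It needs drop-out of 33% versus 15%, and the within-table differences are small. Such an imbalance would show in the denominators and in the tabulation of discontinuations by reason (SAP section 3).
- **That the primary safety conclusion is affected.** The model in Protocol 12.6.1.2 and SAP 5.3.1 compares lenses directly and is not stated to be split by status, although no section that describes it names its analysis set.

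**Conclusion.** The point holds as one of presentation and consistency. On the visible text, AE and slit-lamp percentages are planned by lens only within two sets formed after randomization and partly open to influence by AEs, while the safety analysis set named in Protocol 12.6 is undefined. Comparing lenses within either set is not a randomized comparison.

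Under the assumptions of the worked example, equal true rates of 10% would be shown as 5.3% versus 8.0% among completers and 24% versus 16% among those who discontinued. With equal drop-out and equal AE-driven discontinuation the distortion is zero, and over the other assumed values with 25% drop-out in both arms the Completed gap runs from 2.3 points (2.7% vs 5.0%) to 9.3 points (10.7% vs 20.0%). The documents do not allow the actual size to be stated. No inference is planned on these endpoints and the success criterion does not depend on them. The case for acting is that the correction is nearly free.

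**What to change.** 1. In Protocol 12.2 and SAP section 2, define the safety analysis set as Enrolled Dispensed, grouped by the lens actually exposed. This matches the grouping rule already in SAP section 5.
2. Reconcile Protocol 12.6, Protocol 12.6.2.2 and SAP section 5 so that they name the same sets for the same tables.
3. Add to each AE and slit-lamp table a by-lens column over that set, with counts and percentages. The denominator is eyes for ocular AEs, subjects for nonocular AEs, and eyes examined at the visit for slit-lamp grades.
4. Keep the Completed and Discontinued tables for the ISO/510(k) format, and state that descriptive between-lens safety statements in the study report rest on the pooled column.

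The cost is a few sentences and one column per lens in each table, with no new data. One limit remains: at late visits the pooled slit-lamp column still contains only eyes that were examined. It stops early visits being sorted by later status, but does not replace missing examinations.
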